The duration of response (DOR), which will be estimated using survival analysis methods, is measured from the time measurement criteria are met for CR/PR (whichever is first recorded) until the first date that PD or death is objectively documented (taking as a reference for PD that smallest measurement recorded since the treatment started). Subjects who do not relapse will be censored at the day of their last tumor assessment. The DOR will be estimated separately for each treatment arm. Because the DOR is a conditional estimate (conditional on having a response), comparison between KW-0761 and vorinostat would not be based on randomized groups and therefore will not be made.

The Pruritus Evaluation (Likert scale & Itchy QoL) and Skindex-29, FACT-G and EQ-5D-3L assessments will be summarized at baseline and at the timepoints specified in the study procedures tables for each arm. The improvement (change from baseline) for each of these measures will also be summarized and analyzed using repeated measures ANCOVA utilizing time points through the 6-month assessment.

For those subjects who crossover from the vorinostat arm to the KW-0761 arm, these assessments within the second arm of the study will be measured at the end of the first cycle after the first day of dosing for KW-0761. Baseline measurements for crossover subjects are those documented closest to and before the first KW-0761 infusion. No statistical comparisons will be made for information gathered in the crossover from the vorinostat arm to the KW-0761 arm. All summaries for this arm will be purely descriptive.

Progression-free survival is the primary endpoint in this study. There are four key secondary endpoints in this study that require a comparison between treatment arms: ORR, Skindex-29, FACT-G, and EQ-5D-3L. Comparisons of these four secondary endpoints between the 2 treatment arms will be conducted using p-values that are adjusted to control the overall study-wise Type 1 error rate to be less than 0.05. Since these tests are not independent, the four secondary tests will be conducted using the Sidak adjusted p-value method defined as **Adjusted p-value = $1-(1-p)^4$** where **p** is the original p-value of the individual test

These adjusted p-values will then be compared to .05 for each test.

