6.11.2.4 Analyses of Other Secondary Efficacy Variables

Comparisons between treatment arms for all other secondary endpoints such as Pruritus Evaluation (Likert scale and Itchy QoL) will be conducted with no adjustment for multiple comparisons used for those statistical tests.

PFS and ORR as assessed by the IR will be analyzed using the same method described above for PFS and ORR as assessed by the Investigator.

Frequency tables will be used to display the best overall response as assessed by the Investigator and by the IR during the randomized treatment period for all subjects by treatment arm. The concordance between the investigators assessment and the IR assessment of best overall responses will be presented.

For subjects who achieved a confirmed CR or PR during the randomized treatment period, the time to response will be summarized descriptively. The duration of response will be analyzed using survival analysis methods. The Kaplan-Meier estimate of the median duration of response and the associated 95% confidence intervals will be estimated and presented separately for each treatment arm. Because the DOR is a conditional estimate (conditional on having a confirmed response), comparison between KW-0761 and vorinostat would not be based on randomized groups and therefore will not be made.

The same repeated measures ANCOVA model described above for the analysis of change in Skindex-29 score from baseline to end of cycles 1, 3, and 5 will be performed for the changes in Skindex-29 score, FACT-G total score and EQ-5D-3L index score at other time points up to end of cycle 11. Due to the relatively small sample size of subjects after cycle 11, QoL data beyond cycle 11 will only be summarized descriptively. In addition, for EQ-5D-3L descriptive system, frequency tables will be used to display the number and percentage of subjects with reported problems for each level and for each dimension at each scheduled timepoint.

Other quality of life measurements including changes in Pruritus Evaluation (Itchy QoL score) and EQ-5D-3L VAS score from baseline at each scheduled timepoint up to the cycle 11 assessment will also be analyzed using the same method. The assumptions of normality and homogeneity of variance of the ANCOVA analysis will be examined prior to fitting the models. When significant departure from the assumption is observed, the Wilcoxon rank sum test will be applied.

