For the Pruritus Evaluation Likert Scale data, the changes in the Likert Scale score from baseline at different timepoints up to the cycle 11 assessments during the randomized treatment period will be analyzed using Wilcoxon rank sum test. The treatment difference in the median change of the Likert Scale score from baseline will be estimated using the Hodges-Lehmann estimate and a two-sided 95% confidence interval for the treatment difference will be obtained using the method of Moses.

All quality of life measurements and changes from baseline will be summarized descriptively at each scheduled time point.

For subjects who cross over from the vorinostat arm to the KW-0761 arm, ORR during the crossover portion of the trial will be estimated in a similar fashion as described above for ORR of the randomized therapy. In addition, the quality of life assessments during the crossover portion will be measured at the end of the first cycle after the first day of dosing for KW-0761. Baseline measurements for the crossover portion are considered to be those taken at the last assessment point of the previous cycle. The quality of life measurements as well as the changes from baseline during the crossover portion of the trial will be summarized descriptively. All summaries for the crossover portion will be purely descriptive. No statistical comparisons will be made for data collected during the crossover portion.

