6.11.2.5 Analyses of Exploratory Efficacy Variables

Although not considered a secondary endpoint, a comparison between treatment arms for OS and TTF will be conducted using the same method as described above for the analysis of PFS based on the ITT set and will be considered exploratory.

Additional exploratory analysis will be performed for comparison of PFS between subjects with any exposure to KW-0761 versus subjects with vorinostat only. For this analysis, the PFS for subjects who cross over from the vorinostat arm to KW-0761 will be calculated from the first dose of KW-0761.

Statistical analyses on OS using follow-up data may take place after database lock for the study and will be reported as supplemental to the Clinical Study Report.

The following exploratory analyses will be performed for OS to account for crossover effect:

- The rank-preserving structural failure time (RPSFT) model will be applied to allow a direct comparison of the randomized treatment groups by adjusting the OS of subjects who crossed over so that it reflects the OS had they not received KW-0761.¹²
- The Inverse Probability of Censoring Weighting (IPCW) model will also be applied. In this method subjects who cross over from IC to KW-0761 will be censored and subjects remaining on IC will be weighted to compensate for missing data. The bias introduced by the crossover will be corrected by weighting each subject by the inverse of the predicted probability of not being censored at a given time.¹²

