Note: Hazard ratio, 95% CI, and p-value are obtained from a Cox proportional hazard model with treatment, disease type, disease stage, Blood Involvement, region, age group, gender, and race category as explanatory variables.

<<Programming Note: Backward selection method will be used to identify the final set of prognostic factors (exit p-value is set to be 0.1).
 Treatment will be fixed in the model, i.e., will not be eliminated.>>

The following table will have a similar layout as Table 14.2.1.1:

Table 14.2.1.6.1
Summary of Progression-Free Survival (PFS)
Efficacy Evaluable Set

Table 14.2.1.6.2
 Summary of Progression-Free Survival (PFS)
 Intent-to-Treat Set
 Any Exposure to KW-0761 vs. Vorinostat Only

	KW-0761#			
	Vorinostat N=xxx	Crossover	Randomized to KW-0761 N=xxx	Any KW-0761
By Investigator's Assessment				
Number of Subjects with PFS Event (n, %)	xx (xx.x)	xx (xx.x)	xx (xx.x)	xx (xx.x)
Earliest Contributing Event:				
Progressive Disease	xx (xx.x)	xx (xx.x)	xx (xx.x)	xx (xx.x)
Death	xx (xx.x)	xx (xx.x)	xx (xx.x)	xx (xx.x)
Number of Subjects Censored (n, %)	xx (xx.x)	xx (xx.x)	xx (xx.x)	xx (xx.x)
Progression-Free Survival (months)				
Kaplan-Meier Estimate of PFS				
Q1	xx.x	xx.x	xx.x	xx.x
Median (95% CI)*	xx.x (xx.x, xx.x)	xx.x (xx.x, xx.x)	xx.x (xx.x, xx.x)	xx.x (xx.x, xx.x)
Q3	xx.x	xx.x	xx.x	xx.x
Mean	xx.xx	xx.xx	xx.xx	xx.xx
Standard Deviation	xx.xxx	xx.xxx	xx.xxx	xx.xxx
Median	xx.xx	xx.xx	xx.xx	xx.xx
Minimum	xx.x	xx.x	xx.x	xx.x
Maximum	xx.x	xx.x	xx.x	xx.x
----- Treatment Comparison -----				
KW-0761 vs. Vorinostat**				
Hazard Ratio (95% CI)				xx.x (xx.x, xx.x)
Log rank p-value				x.xxxxx
Rate (%) of Being Alive without Progression for at Least***				
6 months (95% CI)	xx.x (xx.x, xx.x)	xx.x (xx.x, xx.x)	xx.x (xx.x, xx.x)	xx.x (xx.x, xx.x)
12 months (95% CI)	xx.x (xx.x, xx.x)	xx.x (xx.x, xx.x)	xx.x (xx.x, xx.x)	xx.x (xx.x, xx.x)
18 months (95% CI)	xx.x (xx.x, xx.x)	xx.x (xx.x, xx.x)	xx.x (xx.x, xx.x)	xx.x (xx.x, xx.x)
24 months (95% CI)	xx.x (xx.x, xx.x)	xx.x (xx.x, xx.x)	xx.x (xx.x, xx.x)	xx.x (xx.x, xx.x)
Etc.				

Note: Percentage is calculated using the number of subjects in the column heading as the denominator.

* 95% CIs are obtained from SAS proc lifetest using loglog transformation.

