** Hazard ratio and 95% CI are based on Cox proportional hazards model with treatment, disease type, disease stage, and region as covariates. P-value (two-sided) is obtained from a stratified log rank test (one-sided test at 0.025 level or equivalently two-sided test at 0.05 level) with disease type, disease stage, and region as stratification factors.

*** Kaplan-Meier estimate.

For subjects who had KW-0761 treatment, PFS is calculated from the first dose of KW-0761.

Table 14.2.1.6.2
 Summary of Progression-Free Survival (PFS)
 Intent-to-Treat Set
 Any Exposure to KW-0761 vs. Vorinostat Only

	KW-0761#			
	Vorinostat N=xxx	Crossover	Randomized to KW-0761 N=xxx	Any KW-0761
By Independent Review Committee				
Number of Subjects with PFS Event (n, %)	xx (xx.x)	xx (xx.x)	xx (xx.x)	xx (xx.x)
Earliest Contributing Event:				
Progressive Disease	xx (xx.x)	xx (xx.x)	xx (xx.x)	xx (xx.x)
Death	xx (xx.x)	xx (xx.x)	xx (xx.x)	xx (xx.x)
Number of Subjects Censored (n, %)	xx (xx.x)	xx (xx.x)	xx (xx.x)	xx (xx.x)
Progression-Free Survival (months)				
Kaplan-Meier Estimate of PFS				
Q1	xx.x	xx.x	xx.x	xx.x
Median (95% CI)*	xx.x (xx.x, xx.x)	xx.x (xx.x, xx.x)	xx.x (xx.x, xx.x)	xx.x (xx.x, xx.x)
Q3	xx.x	xx.x	xx.x	xx.x
Mean	xx.xx	xx.xx	xx.xx	xx.xx
Standard Deviation	xx.xxx	xx.xxx	xx.xxx	xx.xxx
Median	xx.xx	xx.xx	xx.xx	xx.xx
Minimum	xx.x	xx.x	xx.x	xx.x
Maximum	xx.x	xx.x	xx.x	xx.x
----- Treatment Comparison -----				
KW-0761 vs. Vorinostat**				
Hazard Ratio (95% CI)				xx.x (xx.x, xx.x)
Log rank p-value				x.xxxxx
Rate (%) of Being Alive without Progression for at Least***				
6 months (95% CI)	xx.x (xx.x, xx.x)	xx.x (xx.x, xx.x)	xx.x (xx.x, xx.x)	xx.x (xx.x, xx.x)
12 months (95% CI)	xx.x (xx.x, xx.x)	xx.x (xx.x, xx.x)	xx.x (xx.x, xx.x)	xx.x (xx.x, xx.x)
18 months (95% CI)	xx.x (xx.x, xx.x)	xx.x (xx.x, xx.x)	xx.x (xx.x, xx.x)	xx.x (xx.x, xx.x)
24 months (95% CI)	xx.x (xx.x, xx.x)	xx.x (xx.x, xx.x)	xx.x (xx.x, xx.x)	xx.x (xx.x, xx.x)
Etc.				

Note: Percentage is calculated using the number of subjects in the column heading as the denominator.

* 95% CIs are obtained from SAS proc lifetest using loglog transformation.

** Hazard ratio and 95% CI are based on Cox proportional hazards model with treatment, disease type, disease stage, and region as covariates. P-value (two-sided) is obtained from a stratified log rank test (one-sided test at 0.025 level or equivalently two-sided test at 0.05 level) with disease type, disease stage, and region as stratification factors.

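### The exploratory PFS comparison of any KW-0761 exposure against vorinostat only groups subjects by a post-randomization event, so its hazard ratio is not a treatment effect and its p-value does not hold its level

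*SAP*

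**What the plan says.** SAP 6.11.2.5 plans the comparison: "Additional exploratory analysis will be performed for comparison of PFS between subjects with any exposure to KW-0761 versus subjects with vorinostat only". It then sets the clock for one subgroup: "the PFS for subjects who cross over from the vorinostat arm to KW-0761 will be calculated from the first dose of KW-0761".

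Mock Table 14.2.1.6.2, titled "Any Exposure to KW-0761 vs. Vorinostat Only" and labelled as the ITT set, has columns for vorinostat, crossover, randomized to KW-0761 and any KW-0761. It prints a Cox hazard ratio with 95% CI and a log-rank p-value in the investigator block and again in the independent review block. The footnote says "P-value (two-sided) is obtained from a stratified log rank test" and ties it to one-sided 0.025, or two-sided 0.05. A further footnote reads "For subjects who had KW-0761 treatment, PFS is calculated from the first dose of KW-0761".

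Crossover is governed by Protocol 3.4 and 5.3. A vorinostat subject may cross after progression (routinely from the 8-week assessment, earlier by exception) or for intolerance, if still eligible and with sponsor approval.

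Elsewhere the documents rule this kind of comparison out. SAP 6.11.2.4: "No statistical comparisons will be made for data collected during the crossover portion". Protocol 10.3: "No statistical comparisons will be made for information gathered in the crossover from the vorinostat arm to the KW-0761 arm". SAP 6.11.2.4 also declines to compare duration of response because the "comparison between KW-0761 and vorinostat would not be based on randomized groups and therefore will not be made".

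**The concern.** Group membership is decided by what happens after randomization. A vorinostat subject who crosses leaves the comparator, and the time on vorinostat, with any progression there, leaves the comparison. That subject then contributes a fresh interval to the KW-0761 side. Those left as vorinostat only are the subjects who never crossed: progressors who were ineligible or not approved, plus subjects censored without progression. Removing events raises the apparent PFS of this remainder; removing long event-free intervals lowers it. Which effect wins depends on who crosses and when.

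The time origin is also inconsistent. The text resets the clock for crossover subjects only, while the footnote resets it for everyone given KW-0761. Under the footnote, a subject randomized to KW-0761 but never dosed has no start time, although the ITT set includes that subject.

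At stake is an uninterpretable hazard ratio and p-value, labelled ITT, printed in the study report beside the randomized result. SAP 6.11.2.5 provides crossover methods (RPSFT and IPCW) for OS, but no method and no caveat for this PFS comparison.

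**Working it through.** **Calibration.** The exploratory comparison has no planning figure of its own, so I checked the primary design first. Schoenfeld events for medians 169 and 254 days (HR 169/254 = 0.665), 1:1, one-sided 0.025, 90% power: 4 × (1.960 + 1.282)² / (ln 0.665)² = 253.2, so 254, against the stated 255. Exponential PFS with 24 months' uniform accrual and 12 months' further follow-up gives 254.8 expected events from 288 subjects. The plan's figures reproduce.

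**Mechanism, by hand.** Take both drugs as identical, with exponential hazard λ = ln2/169 per day. Under that accrual and follow-up:
- probability that a vorinostat subject has an event: q = 0.929;
- λ × E[time; event] = 0.763;
- probability of progression before day 56: 1 − 2^(−56/169) = 0.205, contributing 0.023 to the previous quantity.

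Let a fraction p of eligible progressors cross. The any-KW-0761 group keeps hazard λ. The remaining vorinostat-only group has a changed event rate, so the rate ratio is:
- crossing at any time: (q − 0.763p) / (q − qp);
- crossing only from day 56: (q − [0.763 − 0.023]p) / (q − [0.929 − 0.205]p).

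At p = 0.50/0.70/0.85 these give 1.18/1.42/2.01 and 0.99/0.97/0.95. In the first case the bias comes from censored subjects, who cannot cross as progressors and so accumulate in the comparator. In the second, the 20.5% who progress early stay in the comparator as early events and pull the ratio to or below 1.

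**Simulation at true HR 1.00.** Assumptions: 144 per arm, 24 + 12 months, vorinostat median 169 days, KW-0761 started 14 days after progression, one-covariate Cox model, unstratified log-rank, 4,000 trials per setting (2,000 for the last crossing rule). HR is KW-0761 over vorinostat.

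| Crossing rule | Median HR at 50/70/85% crossing | Two-sided rejection at 0.05 |
|---|---|---|
| (a) progression at 8 weeks or later | 0.99/0.96/0.93 | 7/9/15% |
| (b) as (a), plus 15% selected to cross for intolerance | 0.93/0.90/0.84 | 11/17/26% |
| (c) as (a), gamma frailty variance 1, median held at 169 days | 1.11/1.18/1.26 | 12/21/30% |
| (c) as (a), gamma frailty variance 1, mean hazard ln2/169 | 1.22/1.39/1.58 | 28/52/72% |
| (d) progression at any time | 1.18/1.41/1.98 | 22/51/84% |
| Progressors before week 8 cross at half the rate of later ones | 1.06/1.13/1.25 | 8/15/26% |
| Comparison by randomized arm | 1.00–1.01 | 5–6% |

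False findings mostly favor KW-0761 under (a), almost always do so under (b), and run against it under (c) and (d). The simulated (a) and (d) agree with the hand formulas.

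**At the planned HR of 0.665** (2,000 trials per setting), the by-arm analysis returns 0.66–0.67. The exposure comparison returns 0.67/0.65/0.64 under (a) and 0.78/0.95/1.31 under (d).

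**Different settings.** With 317 subjects, stopping at 255 events or 24 months after the last subject, about 10% loss per year and deaths 5% of events, any-time crossing on progression gave null HRs of 1.13/1.29/1.97 at 30/50/80% crossing. One-sided false findings for vorinostat were 0.14/0.42/0.95 against a nominal 0.025. The HR at 50% exceeds the 1.18 above because more subjects are censored, as the mechanism predicts. With 40% assigned an intolerance crossover and progressors crossing only from day 56, the HR was 0.81 and 0.70 at 30% and 80% crossing, with false findings for KW-0761 of 0.39 and 0.60. The by-arm test stayed near 0.025 in these settings.

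**The case against.** The case for leaving the analysis in has five parts.

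- **It is exploratory.** Protocol 10.3 allows exploratory analyses on other subject groupings, and the SAP's Summary of Revisions openly lists this one. That stands, and it limits the consequence. But exploratory status excuses a lack of multiplicity control; it does not turn a comparison of outcome-defined groups into an estimate of treatment effect. Neither 6.11.2.5 nor the Summary of Revisions says that it departs from Protocol 10.3.
- **The no-comparison sentences sit in paragraphs on other endpoints.** They close paragraphs on crossover response and quality of life (SAP) and on patient-reported assessments (Protocol). Their wording is nevertheless general. The duration-of-response reasoning is an analogy, but it fits exactly.
- **The mock vorinostat column may mean the whole arm, with crossovers counted again under KW-0761.** On that reading and without heterogeneity, the null HR is about 1.00 and one-sided error 0.018–0.035. With heterogeneity and crossover on progression only, the HR is 1.04–1.10 and false findings for vorinostat are 0.056–0.126. That reading contradicts the text's vorinostat-only group and puts the same subjects on both sides of a log-rank test.
- **The largest errors come from any-time crossing, which the Protocol treats as an exception.** This is fair. Under the routine rule without heterogeneity, error is 7–15% and the design HR is nearly undisturbed. Adding intolerance crossover or heterogeneity to that rule still gives 11–72%, in opposite directions.
- **The simulations are unstratified and assume the crossover pattern.** True. They show that the bias can be material in either direction; they do not predict its value.

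**Conclusion.** The concern holds. The hazard ratio in Table 14.2.1.6.2 does not estimate a treatment effect, and its p-value does not hold its stated level. The grouping and clock rules establish this without any simulation. The size is conditional on crossover rate, timing, reasons and patient heterogeneity, none of which the documents give. In the settings tabulated, the null HR ran from 0.84 to 1.98 and two-sided error from 7% to 84%; the mildest routine rule gives 7–15%. The crossover counts and reasons planned for Table 14.1.1.2 would help a reader, but would not let anyone recover the size or sign of the bias from the printed hazard ratio. The primary PFS test, its 255-event design and the four Sidak-adjusted secondary tests are unaffected. This is a correction that should be made to one exploratory analysis, not a threat to the trial's main conclusion.

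**What to change.** In SAP 6.11.2.5, delete the sentence announcing the comparison and reword the one after it to introduce a descriptive summary of crossover PFS.

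In Table 14.2.1.6.2:
- remove the hazard ratio, 95% CI and log-rank p-value from the investigator and independent review blocks, with the footnote that supports them in each;
- keep the crossover column as a descriptive Kaplan-Meier summary from first KW-0761 dose;
- drop the ITT label from the title in both blocks and in the SAP Section 9 list, and name the groups actually shown;
- state one time origin, so that the text and both copies of the footnote agree.

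Keep inferential PFS comparisons to the randomized arms. Tables 14.2.1.1 and 14.2.1.8 are the main ones, and the other planned by-arm PFS tables are not affected.

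The cost is a few lines of SAP text and one table shell with its repeated title and footnotes. No data collection changes and no patients are affected.

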6.11.2.6 Adjustment for Covariates

Additional analysis of the treatment effect on PFS and ORR as assessed by the Investigator when adjusted for potential prognostic factors will be carried out using a multivariate Cox proportional hazard model for PFS and a multivariate logistic regression model for ORR. These analyses will be performed based on the PFS and ORR as assessed by the Investigator for the first assigned therapy and the ITT Set. Potential prognostic factors including disease

type (MF or SS), disease stage (IB and II versus III or IV), compartment involvement (blood involvement or no blood involvement), region (US, Japan, Rest of World), age group (<65 or ≥65 years), gender (males or females), and race category (Black or African American, White, Other) will be included as covariates in the multivariate Cox proportional hazard model for PFS and the multivariate logistic regression model for ORR. Backward selection will be used to identify the final set of prognostic factors (exit p-value is set to be 0.1). The final model will then be used to assess treatment effect when adjusted for these important prognostic factors.

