Comparisons between treatment arms for all other secondary endpoints such as Likert scale, and Itchy QoL will be conducted with no adjustment for multiple comparisons used for those statistical tests. Exploratory subset analyses for PFS and any of the secondary endpoints by region, study site, compartment involvement, CCR4 expression status, disease subtypes, and medical history may be conducted. Details of such subset analyses will be provided in the Statistical Analysis Plan. Although overall survival (OS) is not a secondary endpoint, each subject will be followed in this study for a minimum of 2 years to generate information on OS. Using this follow-up information, a comparison between treatment arms for OS will also be conducted and considered exploratory. Statistical analyses on OS using follow-up data may take place after database lock for the study and will be reported as supplemental to the Clinical Study Report.

Randomization will be stratified within the 2 disease types, SS and MF and 2 disease stages IB or II and III or IV. The efficacy analyses described in this section will be conducted as stratified tests but may also be conducted as a subset analysis within each of these disease-type groups and disease stages. Comparison of endpoints between these 2 groups and

stages will be conducted for each treatment assuming adequate sample sizes in the respective groups.

Exploratory analyses based on other subject groupings and with other parameters may also be conducted.

Since the primary endpoint is PFS, the reference median PFS for vorinostat is assumed to be 169 days. The median PFS for KW-0761 therapy is targeted for 254 days, a 50% improvement over this reference median. For a 24-month accrual and 12 month follow-up on the last subject dosed, [Table 10.3-1](#) gives the power and the number of PFS events required to show superior PFS for KW-0761 therapy over vorinostat at the one-sided 0.025 significance level. The ITT set is used for this primary analysis. The same analysis conducted using the Efficacy Evaluable set is considered secondary.

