Under these assumptions, for the ITT population, a total of 255 PFS events will give 90% power (row is in bold in [Table 10.3-1](#)). For this study, the final primary analysis comparing PFS between treatment groups will not be conducted until 255 PFS events occur or until a maximum of 24 months after the last randomized subject's first dose, whichever comes first. In the event that the study is stopped prior to 255 PFS events are observed, the primary test will be performed at less than 90% power under the current assumptions according to [Table 10.3-1](#).

Each of these calculations uses a log-rank test to compare the 2 survival curves. Sample size calculations were computed using SAS software version 9.3 using PROC POWER, Twosamplesurvival test = logrank.

Table 10.3-1 Required PFS Events and Power for Comparison of PFS Kaplan-Maier Curves Between the Vorinostat and KW-0761 Arms at the 0.025 Level

Vorinostat Median PFS = 169 Days, KW-0761 Median PFS = 254 Days		
Power	Total Required PFS Events	Expected Total Sample Size to Achieve The Required Events
90	255	288
89	247	280
88	239	270
87	231	262
86	225	254
85	218	248
84	212	240
83	206	234
82	201	228
81	196	222
80	191	216

The total sample size of 288 represents the approximate number of subjects that may be necessary for 255 PFS events to occur within the projected 36 months of the trial. If a 10% inflation factor is applied to this total (about 29 subjects) to take into account those subjects that may be lost to follow-up prior to documented progression, a total of 317 enrolled subjects may be necessary in order to observe 255 PFS events.

The observed rates of PFS events, recruitment, and drop-outs will be monitored throughout the study and may be used to alter the number of sites, the accrual period, and the follow-up period to achieve the required 255 PFS events in a timely manner. If the 255 PFS events are not observed within 36 months from the start of enrollment the study will be stopped at approximately 24 months after the last randomized subject's first dose.

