6.11.2.7 Subgroup Analyses

Subgroup analyses will be performed for PFS as assessed by the Investigator based on the first assigned therapy for the ITT Set and the Efficacy Evaluable Set provided that there are adequate sample sizes in the respective groups. The following subgroup factors will be used:

- Disease type (MF or SS);
- Disease stage (IB and II versus III or IV);
- Blood involvement (yes or no);
- Region (US, Japan, Rest of World);
- Age group (<65 years or ≥65 years);
- Gender (male or female);
- Race category (Black or African American, White, Other).
- LDH (normal versus elevated)

Forest plot of hazard ratios by subgroups will be provided for PFS as assessed by the Investigator. Additional subgroup analyses may be performed.

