Variable Statistic/Category	Vorinostat N=xxx	KW-0761 N=xxx	Total N=xxx
Prior CTCL Therapy			
Number of Prior CTCL Therapies (n, %)			
1	xx (xx.x)	xx (xx.x)	xx (xx.x)
2	xx (xx.x)	xx (xx.x)	xx (xx.x)
3	xx (xx.x)	xx (xx.x)	xx (xx.x)
4	xx (xx.x)	xx (xx.x)	xx (xx.x)
5	xx (xx.x)	xx (xx.x)	xx (xx.x)
>=6	xx (xx.x)	xx (xx.x)	xx (xx.x)
Best Response to Last CTCL Therapy Prior to Study Entry (n, %)			
Complete response	xx (xx.x)	xx (xx.x)	xx (xx.x)
Partial response	xx (xx.x)	xx (xx.x)	xx (xx.x)
Complete response or partial response	xx (xx.x)	xx (xx.x)	xx (xx.x)
Stable disease	xx (xx.x)	xx (xx.x)	xx (xx.x)
Progressive disease	xx (xx.x)	xx (xx.x)	xx (xx.x)
Not applicable	xx (xx.x)	xx (xx.x)	xx (xx.x)
Unknown	xx (xx.x)	xx (xx.x)	xx (xx.x)
Prior Radiotherapy (n, %)			
No	xx (xx.x)	xx (xx.x)	xx (xx.x)
Yes	xx (xx.x)	xx (xx.x)	xx (xx.x)
CCR4 Expression Status (n, %)			
Positive	xx (xx.x)	xx (xx.x)	xx (xx.x)
Negative	xx (xx.x)	xx (xx.x)	xx (xx.x)
Unknown	xx (xx.x)	xx (xx.x)	xx (xx.x)

Note: Percentage is calculated using the number of subjects in the column heading as the denominator.

[1] Baseline is defined as the last measurement obtained prior to the first dose of study drug.

* Time from initial diagnosis (months) is calculated as (date of first dose of study medication - date of initial diagnosis + 1)/30.
 If the month and year of the diagnosis are provided but the day is missing, the missing day is imputed as 15. If only the year is provided, then the missing month and day are imputed as July 1 for the calculation.

Table 14.1.2.1
 Demographic and Baseline Disease Characteristics
 Intent-to-Treat Set

Variable Statistic/Category	Vorinostat N=xxx	KW-0761 N=xxx	Total N=xxx
LDH (U/L) at Baseline			
n	xx	xx	xx
Mean	xx.x	xx.x	xx.x
Std Dev	xx.xx	xx.xx	xx.xx
Median	xx.x	xx.x	xx.x
Minimum	xx	xx	xx
Maximum	xx	xx	xx

Note: Percentage is calculated using the number of subjects in the column heading as the denominator.

[1] Baseline is defined as the last measurement obtained prior to the first dose of study drug.

* Time from initial diagnosis (months) is calculated as (date of first dose of study medication - date of initial diagnosis + 1)/30. If the month and year of the diagnosis are provided but the day is missing, the missing day is imputed as 15. If only the year is provided, then the missing month and day are imputed as July 1 for the calculation.

The following tables will have a similar layout as Table 14.1.2.1:

Table 14.1.2.2

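### Baseline LDH is a pre-specified PFS subgroup factor but not a candidate covariate in the supportive adjusted PFS model; add it, or say why it is left out.

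*SAP*

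**What the plan says.** - **Adjusted models.** SAP 6.11.2.6 plans a multivariate Cox model for PFS and a logistic model for ORR, both on investigator assessment in the ITT set. The candidates are disease type, stage, blood involvement, region, "age group (<65 or ≥65 years), gender (males or females), and race category (Black or African American, White, Other"). Backward selection uses an exit p-value of 0.1. The note under Table 14.2.1.5 keeps treatment in the model throughout.
- **Table shells.** The Table 14.2.1.5 footnote names treatment and disease type, then "disease stage, Blood Involvement, region, age group, gender, and race category as explanatory variables". The Table 14.2.2.1.2 footnote (ORR) has the same list. The lead-in in 6.11.2.6 could be read as open-ended, but the footnotes are closed lists, and LDH is in neither.
- **Subgroups.** SAP 6.11.2.7 lists those seven factors for PFS and adds "LDH (normal versus elevated"). The programming note under Table 14.2.1.7.1 repeats LDH.
- **Data.** LDH is in the chemistry panel (Protocol Table 7.1.1-1). The baseline table shell (SAP Table 14.1.2.1) summarizes "LDH (U/L) at Baseline" by arm.
- **Room for more.** SAP 6.11.2.1 and 6.11.2.3 permit further adjusted analyses using other baseline characteristics, but name none.

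**The concern.** The two PFS lists sit in adjacent sections and differ by one item. A variable thought important enough for splitting the PFS result is absent from the model meant to show that the result survives adjustment, and the SAP does not explain the difference.

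Two things could be lost if LDH is prognostic. First, in a Cox model, leaving out a prognostic covariate moves the treatment log hazard ratio toward zero even when the arms are balanced, so the supportive analysis has less power than the data allow. Second, if the arms differ on LDH by chance, no named model yields one overall LDH-adjusted hazard ratio. An LDH adjustment chosen after the imbalance is seen, in an open-label trial, carries less weight than one fixed in advance.

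**Working it through.** **1. The planned effect.** From Protocol 10.3: "the reference median PFS for vorinostat is assumed to be 169 days"; "The median PFS for KW-0761 therapy is targeted for 254 days"; test at the "one-sided 0.025 significance level"; 1:1 allocation; "a total of 255 PFS events will give 90% power".

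- HR = 169/254 = 0.665; ln HR = −0.407.
- Schoenfeld events = 4 × (1.960 + 1.282)² / 0.407² = 254.
- Power at 255 events = Φ(0.407 × √255 / 2 − 1.960) = 90.2%.

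The plan's figure reproduces, so this effect is a fair base for the comparison.

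**2. Effect of adding LDH to the PFS model.** Cox models were fitted to simulated trials: 317 subjects, exponential PFS, 24 months' uniform accrual plus 12 months' follow-up, light loss to follow-up, about 255 to 260 events on average, 2,000 runs per setting. Assumptions not in the documents: 45% with elevated LDH, independent of the other variables; elevated-LDH HR 1.0 to 2.0; age mean 64, SD 12. Both models contain treatment and age cut at 65; one adds elevated LDH. The rows below assume age itself has no effect.

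| LDH HR (assumed) | Mean log HR, without → with LDH | SE, without → with | Power, without → with |
|---|---|---|---|
| 1.0 | −0.411 → −0.412 | 0.1261 → 0.1265 | 91.2% → 91.4% |
| 1.3 | −0.406 → −0.412 | 0.1263 → 0.1267 | 90.6% → 90.6% |
| 1.5 | −0.398 → −0.411 | 0.1262 → 0.1267 | 88.0% → 89.8% |
| 2.0 | −0.380 → −0.410 | 0.1266 → 0.1273 | 84.8% → 90.1% |

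At LDH HR 2.0 the hazard ratio is exp(−0.380) = 0.68 without LDH and exp(−0.410) = 0.66 with it. The SE rises by about 0.3% to 0.6%. With an age HR of 1.2 per 10 years, the power gains are 0.2, 0.5, 1.6 and 4.5 points, so the range is again about 0 to 5.

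**3. Chance imbalance, same assumptions.** With 158 and 159 subjects per arm, the SE of the difference in proportion elevated is √(0.45 × 0.55 × (1/158 + 1/159)) = 0.056, so the 95% chance range is ±1.96 × 0.056, about ±11 points. The approximate shift in log HR at that limit is ln(LDH HR) × 0.11:

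- LDH HR 1.0: none.
- LDH HR 1.5: 0.405 × 0.11 = 0.045, about 0.35 SE. An HR of 0.665 would read as about 0.695 if the imbalance went against KW-0761.
- LDH HR 2.0: 0.693 × 0.11 = 0.076, about 0.6 SE. It would read as about 0.72.

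The shift can equally go the other way. Stratification by type and stage would narrow it if LDH tracks them.

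**4. Neighbouring choices, for scale.** Continuous age instead of the cut at 65 left the SE unchanged to within 0.0001 and moved power by between −0.6 and +1.4 points, mostly simulation error. Adding LDH to the ORR logistic model (assumed response rates about 10% and 25%, odds ratio for non-response 1.0 to 3.0, 1,000 runs per setting) gained 0 to about 1 point. The SE rose from 0.329 to 0.330 at odds ratio 1.0 and from 0.318 to 0.325 at 3.0.

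**The case against.** The case for leaving the model alone has real substance.

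- **A subgroup factor need not be a covariate.** Subgroups examine consistency of the treatment effect; adjustment uses prognostic factors. No readable text calls LDH prognostic, and the background sections are redacted. This stands as a limit on the size of the point, but not as a reason for silence: every other subgroup factor in 6.11.2.7 is also a covariate.
- **The simulation is simpler than the SAP model.** It leaves out type, stage, blood involvement, region, gender, race and backward selection, and treats LDH as independent of them. Overlap with stage or blood involvement would shrink the gain, so 5 points is toward the upper end for an HR of 2.0.
- **Nothing is decided on this model.** It has no alpha and no success rule. The primary test is the log-rank stratified by type, stage and region. This stands and keeps the point minor.

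A reader might also infer more than the documents support:

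- *That the adjusted estimate gives up precision.* It does not; the SE is slightly smaller without LDH. What changes is the distance of the estimate from zero. The hazard ratio without LDH is also not invalid: it averages over LDH rather than conditioning on it.
- *That an LDH imbalance could not be addressed at all.* Table 14.1.2.1 would show it, the subgroup tables give hazard ratios within normal and elevated LDH, and 6.11.2.1 allows further adjustment. What is missing is a named, pre-specified model.
- *That the ORR model has the same inconsistency.* LDH is a subgroup factor for PFS only.
- *That the age cut costs much.* It has almost no effect here and matches the cuts used elsewhere in the SAP.

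**Conclusion.** The point holds for the PFS model: LDH is the only PFS subgroup factor missing from the adjustment list, it is already collected, and no reason is given. The consequence is attenuation of the supportive adjusted hazard ratio and a power loss of about 0 to 5 points, plus the lack of a named model for a chance LDH imbalance. Both depend on an assumed elevated-LDH HR of 1.0 to 2.0 at 45% prevalence. If LDH is not prognostic, nothing is lost. Stronger assumed effects would give larger losses, but the documents offer no basis for choosing one. The primary analysis and the design figures do not depend on this list, so this is a worthwhile tidy-up rather than a flaw in the trial.

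**What to change.** In SAP 6.11.2.6 and the Table 14.2.1.5 footnote, add baseline LDH as a candidate covariate in the PFS Cox model, or state why it is excluded. Scale it to the local upper limit of normal, for example log(LDH/ULN): SAP 6.12.2 says local laboratories were used, so raw U/L values may not be comparable between sites. Keep the normal/elevated split for the subgroup display.

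Add one sentence on missing baseline LDH so that the ITT set is kept, for example imputing the median of log(LDH/ULN) pooled over both arms. The number affected is not in the documents and is presumably small.

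Optional, with little expected effect: add LDH to the ORR logistic model (Table 14.2.2.1.2) for consistency, and enter age as continuous.

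The cost is one covariate, a footnote edit and a missing-data sentence, with no new data collection. The planned backward selection will usually drop LDH if it is uninformative.
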